- Active thrombosis, or a history of deep vein thrombosis or pulmonary embolism, within 4 weeks prior to C1/D1, unless adequately treated and stable
- Active uncontrolled bleeding or a known bleeding diathesis
- Significant gastrointestinal abnormalities
- Significant cardiovascular disease or condition
- Abnormal hematologic, renal or hepatic function as defined by the following criteria:
 - a. Absolute neutrophil count (ANC) $< 1.5 \times 10^9 / L (1500 / mm^3)$
 - b. Hemoglobin ≤8 g/dL
 - c. Platelet count $<100 \times 10^9/L (100,000/mm^3)$
 - d. Serum creatinine $>1.5 \times$ upper limit of normal (ULN) for the institution
 - e. Aspartate aminotransferase (AST) $> 3.5 \times ULN$ for the institution or AST $> 5 \times ULN$ for the institution in case of known liver metastases
 - f. Alanine aminotransferase (ALT) > 3.5 \times ULN for the institution or ALT >5 \times ULN for the institution in case of known liver metastases
 - g. Total bilirubin $> 1.5 \times ULN$ for the institution
 - h. Prothrombin time (PT) as assessed by International Normalized Ratio (INR) >1.5 × ULN for the institution*
 - i. Partial thromboplastin time (PTT) >1.5 × ULN for the institution*
 *Unless on a stable dose (per the Investigator's discretion) of anticoagulant therapy for a prior thrombotic event
- Any of the following within 2 weeks prior to C1/D1:
 - a. Any serious or uncontrolled infection
 - b. Any infection requiring parenteral antibiotics
 - c. Unexplained fever >38.0 °C

Confidential Page 14 of 156

Investigational Medicinal Product: Dose(s) and Treatment

Schedule

Pan-HER will be initiated on C1/D1 and, based on cohort assignment, will be administered either Q1W or Q2W to separate dose-escalation cohorts of patients by IV infusion in cycles of treatment:

- Q1W: Dosing on Day 1, 8, 15, and 22 of each 28-day cycle (±2 days)
- Q2W: Dosing on Day 1 and 15 of each 28-day cycle (± 2 days)

All patients will receive the allocated dose and schedule of Pan-HER until treatment withdrawal. There will be no intra-patient dose-escalation. Dose-delays of Pan-HER and/or intra-patient dose-reduction(s) may be required upon occurrence of specific toxicities.

For Part 1 of the trial, Pan-HER will be administered following delivery of intensive prophylaxis, as defined herein, on a mandatory basis to reduce the risk of IRRs and oropharyngeal mucositis.

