5.3.3 Treatment

On the day of the first scheduled Pan-HER infusion (C1/D1), and prior to the start of infusion (SOI), the Investigator must assess whether any changes have occurred in the clinical state of the patient, which would exclude the patient from the trial.

Pan-HER will be administered by IV infusion on either a Q1W or a Q2W schedule:

- Q1W: dosing will be every 7 (±2) days. Four (4) doses of Pan-HER administered Q1W constitute 1 cycle.
- Q2W: dosing will be every 14 (±2) days. Two (2) doses of Pan-HER administered Q2W constitute 1 cycle.

Patients in Part 1 will be enrolled to either Q1W or Q2W dose-escalation cohorts until establishment of an MAD, an MTD, and/or a RP2D for each schedule.

During Part 2, all patients will receive the RP2D and regimen of Pan-HER.

For all patients, the dose and schedule to be administered will be documented on the Screening and Allocation Form. Patients will receive the allocated dose and schedule according to their cohort assignment until treatment withdrawal. There will be no intra-patient dose-escalation. Dose-delays of Pan-HER and/or intra-patient dose-reduction(s) may be required upon occurrence of specific toxicities, as described in **Section 7.1.4**.

Treatment will continue until unacceptable toxicity or other conditions preventing further treatment, progressive disease (PD), termination of the trial, or patient's decision to withdraw.

Disease status evaluation will be by computed tomography (CT) or magnetic resonance imaging (MRI) according to Response Evaluation Criteria in Solid Tumors (Version 1.1) (RECIST v1.1) (22).

Confidential Page 41 of 156

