5.3.5 Schedule of Assessments

Schedule of Assessments are provided in Table 2 (Q1W dosing) and Table 3 (Q2W dosing).

Visit windows are included. The projection of visit days within each cycle must be made from Day 1 of the respective cycle. Furthermore, each new cycle must be initiated as soon as possible after completion of the previous cycle to maintain the dosing schedule.

All individual assessments are to be performed on or about the indicated visit day (i.e., ± 2 days) unless otherwise stated. All efforts should be made to perform assessments as close as possible to the scheduled time points.

Confidential Page 42 of 156

Table 2 Schedule of Assessments: Q1W Dosing

Pre-Treatment Period						Treatment Period ¹						Post-Treatn	nent Period ²				
	Screening			Cycle 1	l			Су	cle 2, 4,	6 etc.		(Cycle 3,	5, 7 etc		EOT	1M FUP
Day within Cycle Visit Window (± days)	D-14 to D-1	D1	D3	D8 (±2)	D15 (±2)	D22 (±2)	D1 (±2)	D8 (±2)	D15 (±2)	D22 (±2)	End of Cycle	D1 (±2)	D8 (±2)	D15 (±2)	D22 (±2)	≤ 10 d from the decision of trial treatment withdrawal	1 month after last dose of trial treatment (30+7d)
Informed Consent ³	X																
Baseline Characteristics ⁴ /Eligibility	X	X															
Safety Assessments																	
Medication/Procedure Survey	X	X	X	X	X	X	X	X	X	X	X	X	X	X	X	X	X
(S)AE Survey and Reporting	X	X	X	X	X	X	X	X	X	X	X	X	X	X	X	X	X
DLT Evaluation ⁵ Part 1 only		X	X	X	X	X	C2 only										
Vital Signs and Body Measurements	X	X		X	X	X	X	X	X	X		X	X	X	X	X	X
ECOG PS ⁶	X	X^6					X					X				X	X
Physical Examination ⁶	X	X^6					X					X				X	X
ECG ⁷	X															X	
ECHO or MUGA scan ⁸	X															X	
Safety blood samples ^{6,9}	X	X ⁶	X	X	X	X	X		X			X		X		X	X
Urinalysis ^{6,9}	X	X^6			X		X					X				X	X
Pregnancy Test	X															X	
Complement Panel ¹⁰ Part 2 only		X															
Disease Assessments																	
Disease Status Evaluation by CT/ MRI ^{11,12}	X										X					X^{12}	X^{12}
Tumor Marker Evaluation, if applicable ¹³	X										X					X	X
Archival Tumor Tissue ¹⁴ Part 1: Submit if available (optional)	X																
Additional Assessments																	
PK Samples ¹⁵		X	X	X	X	X	X	X	X	X		X	X	X	X	X	X
ADA Sample		X					C2 only					X				X	X
Skin Biopsy ¹⁶	X			X	X		-										
Tumor Biopsy ¹⁷																	
Part 1: Optional	X										C2 only						
Part 2: Required																	
Biomarker Blood Sample ¹⁸	X										C2 only					X	
Trial Treatment																	
Pan-HER Premedication ¹⁹		X		X	X	X	X	X	X	X		X	X	X	X		

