 - A CT/MRI performed within 28 days prior to C1/D1 can be used for evaluation of eligibility and as baseline scan, provided that the CT/MRI has been performed according to the clinical trial protocol requirements.
 - The first CT/MRI assessment for response is done at the end of Cycle 2 and thereafter repeated at the end of every second cycle (in the week prior to Day 1 of the next cycle).
 - In the event of suspected PD, a CT/MRI is to be performed as soon as possible.
 - In the event of CR/PR, a confirmatory CT/MRI is to be performed 28 (+7) days after the first assessment of CR/PR.
- 12) A CT/MRI at EOT should only be performed if the previous CT/MRI has been performed >3 weeks before; a CT/MRI scan at 1M FUP should only be performed if no CT/MRI documents disease progression before or at EOT.
- 13) Tumor marker evaluation to include tumor markers that are part of the trial site standard practices as indicated by tumor type, if applicable.
- 14) Archival tumor tissue, **applicable for patients in Part 1 only if tissue is available**: To be assessed locally, preferably by immunohistochemistry (IHC). Does not need to be repeated if EGFR and HER2 status have been assessed previously and the pathology report is available to document findings.
- 15) Extended PK sampling for PK profiling will be done starting C1/D1 and C1/D22. Refer to Table 11 for further details.
- 16) Skin biopsy: All patients enrolled will undergo skin biopsies. Sample is to be obtained during screening after patient eligibility has been confirmed. Sampling is to be repeated Cycle 1/Day 8 (prior to dosing) and Cycle 1/Day 15 (prior to dosing).
- 17) Tumor biopsy, **Optional for patients in Part 1. Required for all patients in Part 2:** To be assessed centrally. Tumor biopsy is to be performed after patient eligibility has been confirmed. Archival tissue may be accepted at screening if suitable for central analysis. Sampling is repeated at the end of Cycle 2 or upon PD, whichever occurs first. Refer to **Section 8.7** for further details.
- 18) Biomarker blood sample: To be obtained during screening after patient eligibility has been confirmed. Sampling is to be repeated at the end of Cycle 2 or upon PD, whichever occurs first, and at EOT.

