7.1.4.2 Dose-Delays for Pan-HER-Related or Disease-Related Toxicities

Clinical judgment will be used when determining whether it is advisable to continue a patient on to the next dosing. In order to dose a patient, the following retreatment criteria must be met. Evaluations must occur at minimum prior to each Cycle 1 dose and prior to D1 and D15 doses each cycle thereafter:

- 1. ANC $> 1.5 \times 10^9 / L (1500 / mm^3)$
- 2. Platelet count >75 $\times 10^9$ /L (75,000/mm³)
- 3. Any ongoing AEs should NOT meet the criteria for DLT, during the DLT-observation period
- 4. Any ongoing AEs, assessed as possibly, probably, or related to Pan-HER, should have either ameliorated to ≤ Grade 1 severity, returned to baseline status, or resolved with the exception of Grade 2 clinical events that are being adequately controlled with best supportive care (e.g., nausea, vomiting, diarrhea, fatigue) and asymptomatic laboratory abnormalities that are considered clinically insignificant or that are resolving with medical therapy

Should any one of the criteria above not be met, dosing of Pan-HER must be delayed until the patient meets the above criteria. All per protocol assessments must be done.

Confidential Page 64 of 156

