8.3 Disease Assessments

8.3.1 Disease Status Evaluation by CT or MRI

The anti-tumor activity of Pan-HER will be assessed by the Investigator, or qualified designee, according to RECIST v1.1. Refer to **Appendix 1**.

Patients will undergo imaging by CT or MRI of neck, chest, abdomen and pelvis as indicated based on tumor type and clinical judgment in order to follow the underlying malignancy. The use of CT or MRI must be consistent per patient throughout the trial. Use of contrast is preferred but is at the discretion of the Investigator, as medically indicated.

Screening

Note: A CT/MRI performed within 28 days prior to Day 1 may be used for evaluation of eligibility and as baseline scan, provided that the CT/MRI has been performed according to the protocol requirements.

Confidential Page 78 of 156

- End of Cycle 2 and end of every second cycle thereafter, i.e., Cycle 4, 6, 8 etc.

 Note: End of cycle assessments may be conducted at any time during the week prior to Day 1 of the next cycle.
- Suspected PD (as soon as possible)
- Confirmation of response, to be performed 28 (+7) days after the first assessment of CR/PR
- EOT (if >3 weeks since previous CT/MRI)
- At 1M FUP (if PD was not documented before or at EOT)

If PD is documented at any time, no further disease assessments will be required. Patients with documented PD will be discontinued from Pan-HER so that alternative management of their malignancy may be considered.

To be assigned a status of confirmed PR or CR, changes in disease status must be confirmed by repeat imaging studies performed no less than 28 days (4 weeks) after the criteria for response are first met. In the case of SD, follow-up measurements must have met the SD criteria at least once after trial entry at a minimal interval in general no less than 6-8 weeks from first dose of Pan-HER.

Imaging data (imaging studies and derived assessments) will be stored by the trial sites and will be available upon request for potential review by the Sponsor or an independent radiology reviewer. For Part 2 only: In addition, imaging studies will be sent to an imaging facility for storage to ensure central availability and readiness for read at a future time upon Sponsor or Health Authority (HA) request.

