4.10.2.1 Anti-Tumor Response according to RECIST v1.1

The following anti-tumor response endpoints will be measured in Part 1:

- Confirmed and unconfirmed BOR by RECIST v1.1 will be listed and summarized by dose regimen and dose level received using frequency distribution for the categories CR, PR, SD, PD, and Not Evaluable.
- Number and percentage of patients with documented confirmed and unconfirmed OR will be summarized by dose regimen and dose level using frequency distribution with the corresponding 95% exact Clopper-Pearson Confidence Intervals (CI) for binomial proportion. All documented ORs will be listed including duration (weeks) of response.
- Patients in DCR will be listed and summarized by dose regimen and dose level using frequency distribution with the corresponding 95% exact Clopper-Pearson Confidence Intervals (CI) for binomial proportion.
- Time to Progression (TTP)

PAREXEL International
Statistical Analysis Plan Template for Early Phase Studies

Symphogen A/S
Sym013-01

The median TTP, as well as 26 weeks and 52 weeks TTP rates and the corresponding 95% CIs will be estimated using the product-limit method and presented using a Kaplan-Meier plot. Number and percent of censored patients will be presented, also number and percent of patients censored for death will be presented.

- Changes in sum of diameters of target lesions from baseline to end of trial participation
Changes in the sum of diameters of target lesions from baseline to end of trial participation will be listed as percentage and absolute value, the best change (i.e., largest reduction or smallest increase) will be identified and presented using summary table and plotted with a waterfall plot. Change in sum of diameters will also be presented by primary tumor type.
- Results of the tumor evaluation by CT/MRI for target lesions, non-target lesions and timepoint tumor response will be listed, as well as derived target and non-target time point responses.

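### Tumour scans follow the cycle count, so a held dose can push the next scheduled scan later and carry a patient past the 16-week disease-control cut

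*Protocol*

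**What the plan says.** **Scan timing.** Protocol Tables 2 and 3, footnote 11: "The first CT/MRI assessment for response is done at the end of Cycle 2 and thereafter repeated at the end of every second cycle". Section 8.3.1 sets the window: "End of cycle assessments may be conducted at any time during the week prior to Day 1 of the next cycle". SAP 3.2.1.1 repeats both.

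**What a cycle is.** Protocol 5.3.3: "Four (4) doses of Pan-HER administered Q1W constitute 1 cycle"; for Q2W it is two doses. SAP 4.9 counts a cycle as completed only when all its infusions were received. Protocol 5.3.5 adds that "each new cycle must be initiated as soon as possible after completion of the previous cycle to maintain the dosing schedule", and projects visit days from Day 1 of each cycle, not from C1/D1. The Synopsis, however, also gives a length: "Q1W: Dosing on Day 1, 8, 15, and 22 of each 28-day cycle (±2 days").

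**Holds.** Protocol 7.1.4.2: "dosing of Pan-HER must be delayed until the patient meets the above criteria. All per protocol assessments must be done". There is no skip rule and no stated maximum. Section 9.5.1 foresees delays of more than 2 weeks, as a DLT criterion.

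**Scans that do not depend on cycle.** A scan is required as soon as possible on suspected progression (PD), at end of treatment (EOT) if the last one was more than 3 weeks earlier, and at the 1-month follow-up (1M FUP) if PD is not yet documented.

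**Analysis.** SAP 3.2.1.1 computes TTP in weeks as (date of PD − date of first infusion + 1) / 7. It uses the same time to decide whether stable disease lasted at least 16 weeks for DCR. SAP 4.10.2.1 plans "The median TTP, as well as 26 weeks and 52 weeks TTP rates" by the product-limit method. Under SAP 4.2 the default presentation is by regimen and dose group. No analysis allows for scan timing.

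**The concern.** Progression is dated by the scan that finds it. If a hold delays the scan, the timing of assessment depends on tolerability. Two patients with the same tumour course can then have different recorded TTP, or fall on different sides of the 16-week cut, only because one had a dose held. Tolerability may differ by dose and schedule, so the schedule of looks may differ between the columns of the TTP and DCR tables. Those tables (14.2.4.1 and 14.2.4.2) and the Kaplan-Meier figure (14.2.29) are all flagged for the abbreviated study report.

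**Working it through.** **1. How the plan itself treats a delay.** The relative dose intensity example in SAP 4.9 has eight Q2W doses with one 1-week delay:

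100 × [(12 + 5×9 + 2×6)/119] / [(12 + 7×9)/112] = 100 × (69/119)/(75/112) = 86.6%, which matches the SAP.

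The planned span is 7×14 + 14 = 112 days and the actual span is 7×14 + 7 + 14 = 119. The delay is added calendar time; no dose is dropped.

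**2. Scan windows.** Let h be the cumulative hold in days. Day 1 of the cycle after cycle k falls on day 28k + 1 + h, so the scan window is days 28k + h − 6 to 28k + h. A PD found on study day d gives TTP = d/7 weeks. The ±2-day dosing window is ignored.

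| Scan | No hold | 1 week | 2 weeks | 3 weeks | 4 weeks |
|---|---|---|---|---|---|
| End of Cycle 2 | 7.1–8.0 | 8.1–9.0 | 9.1–10.0 | 10.1–11.0 | 11.1–12.0 |
| End of Cycle 4 | 15.1–16.0 | 16.1–17.0 | 17.1–18.0 | 18.1–19.0 | 19.1–20.0 |
| End of Cycle 6 | 23.1–24.0 | 24.1–25.0 | 25.1–26.0 | 26.1–27.0 | 27.1–28.0 |

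Take a patient stable at the Cycle 2 scan with PD at the Cycle 4 scan. Without a hold, the scan falls on days 106–112 and the patient misses the 16-week cut unless scanned on day 112. With one cumulative week of hold it falls on days 113–119 and the patient always passes. Three cumulative weeks carry the Cycle 6 scan past the 26-week landmark.

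**3. Share with recorded TTP of at least 16 weeks.** The documents give neither a TTP distribution nor a hold frequency, so this step is an assumption. True TTP is exponential with median m, so S(t) = 2^(−t/m). Scans are at mid-window, and the same hold recurs in every two cycles. With scheduled scans only, the share equals S at the last scan before week 16. That scan is at 15.5 weeks with no hold, and at 8.5, 9.5 or 11.5 weeks with 1, 2 or 4 weeks of hold per two cycles.

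| m (weeks) | True S(16) | No hold | 1 week | 2 weeks | 4 weeks |
|---|---|---|---|---|---|
| 6 | 15.7% | 16.7% | 37.5% | 33.4% | 26.5% |
| 8 | 25.0% | 26.1% | 47.9% | 43.9% | 36.9% |
| 12 | 39.7% | 40.8% | 61.2% | 57.8% | 51.5% |
| 16 | 50.0% | 51.1% | 69.2% | 66.3% | 60.8% |

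If half of PD is instead found within half a week by suspected-PD scans, the m = 6, 1-week figure falls to 0.5×37.5 + 0.5×16.7 = 27.1%.

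**4. TTP outputs.** Same model with m = 12 and scans at exact multiples of L weeks. The landmark rate is S at the last scan on or before the landmark. The median is the first scan with S ≤ 0.5. The mean is L/(1 − 2^(−L/12)).

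| Hold per two cycles | L | 26-week rate | 52-week rate | Median | Mean |
|---|---|---|---|---|---|
| 0 | 8 | S(24) = 25.0% | S(48) = 6.25% | 16 | 21.6 |
| 1 week | 9 | S(18) = 35.4% | S(45) = 7.4% | 18 | 22.2 |
| 2 weeks | 10 | S(20) = 31.5% | S(50) = 5.6% | 20 | 22.8 |
| 4 weeks | 12 | S(24) = 25.0% | S(48) = 6.25% | 12 | 24.0 |
| Truth | – | 22.3% | 5.0% | 12 | 17.3 |

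Only the mean rises steadily with the hold, and the mean is not a planned output. The planned median and landmark rates jump with the scan grid and can fall. In the mid-window model with m = 8, the median drops from 15.5 weeks (S(7.5) = 52.2%) to 8.5 weeks (S(8.5) = 47.9%) with a 1-week hold.

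**5. Patients who stop.** A patient whose only dose is C1/D1 has the 1M FUP scan on days 31–38, at 4.4–5.4 weeks. That is earlier than the first scheduled scan at 7.1–8.0 weeks.

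**The case against.** **The mechanism is inferred.** No passage says imaging moves with a hold. The cycle is also called a 28-day cycle, all protocol assessments remain due when dosing is delayed, and Protocol 5.3.5 asks for assessments close to their scheduled times. This stands as an ambiguity. It does not rescue calendar timing: the imaging window is itself defined by Day 1 of the next cycle, that cycle starts after the previous one is complete, and the SAP's own example adds the delay to the calendar.

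**Direction.** A reader might infer that more toxic dose groups will show inflated TTP. The documents do not support that. Suspected-PD scans shrink the effect, patients who stop for toxicity may be scanned earlier, and steps 3 and 4 show that larger holds need not give larger rates or medians. Nor is it safe to argue that Q1W has twice the hold opportunities. It has twice the doses, but from Cycle 2 the minimum retreatment checks are Day 1 and Day 15 on both schedules.

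**Consequence.** A reader might also infer that TTP feeds the choice of regimen. It does not: Protocol 5.1 and 7.1.3.2 and SAP 3.1 rest that choice on tolerability or safety, PK and target engagement. Part 2 never took place. Duration of response is only listed.

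**Little depends on it.** The primary endpoint is DLTs, and SAP 4.10.1.2 makes all analyses descriptive. Protocol 3.2.4.1 shows groups of 1, 1, 4, 3, 7 and 3 patients as of Amendment 6. The planned listings and swimmer plot should already show scans and dosing per patient. All of this stands and limits the weight of the point, but a listing does not correct a summary rate.

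**Conclusion.** The point holds in a limited form. On the best-supported reading, a hold delays the next scheduled scan by the length of the hold. In patients who stay on treatment with held doses, PD can then be dated later, and nothing in the SAP allows for it. The clearest effect is on the 16-week DCR, because the on-schedule Cycle 4 window ends exactly at the cut and one cumulative week of hold is enough to cross it. That follows from the schedule alone.

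The size does not. The shares in step 3 rest on an assumed exponential TTP with a median of 6 to 16 weeks, an assumed recurring hold, and detection mainly at scheduled scans. They cover only the TTP component of DCR; patients with confirmed CR or PR count regardless. Neither the net direction by dose group nor the size in this trial can be settled from the documents. The affected endpoints are secondary and descriptive, so this is a cheap improvement to interpretation, not a threat to the trial's main conclusion.

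**What to change.** **Schedule (any patient still being scanned, or a successor protocol).** In footnote 11 of Protocol Tables 2 and 3, Section 8.3.1 and SAP 3.2.1.1, time scans every 8 weeks from C1/D1, keeping the present 7-day window, regardless of dose delays. The windows then stay at weeks 7.1–8.0, 15.1–16.0 and 23.1–24.0 for everyone. Reconcile the dose-count and 28-day descriptions of a cycle in the same edit. No change to the hold rule is proposed.

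**Analysis of data already collected.** Enrolment has stopped, so this part matters most now.
- Tabulate actual scan times and cumulative dose delay by regimen and dose group.
- Add an interval-censored TTP analysis using the last non-PD scan and the PD scan. Pool patients or group by regimen, because the dose groups are too small.
- Repeat the 16-week DCR by nominal scan or by last non-PD scan date. Calendar timing alone leaves the cut on the edge of the window.

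**Cost.** Planned scan frequency is the same as with undelayed dosing, but some scans will fall outside dosing visits. The analysis needs one extra table and two sensitivity analyses on dates already captured; SAP Section 1 allows such revisions if documented.
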